#### **Data analysis:**

##### **Statistical Analysis**

We will assess the balance of two randomized groups (McGrath videolaryngoscopy vs. direct laryngoscopy) on **baseline and demographic characteristics** using the absolute standardized difference (ASD), defined as the absolute difference in means, mean ranks, or proportions divided by the pooled standard deviation. Any characteristics with  $ASD > \text{maximum of } 0.10 \text{ and } 1.96 \sqrt{\frac{(n_1 n_2)}{n_1 + n_2}}$  will be considered imbalanced and will be adjusted for in the primary and secondary analyses.

**Formatted:** Font: Bold

All primary and secondary analyses will be completed using the modified intent-to-treat principle, thus including all randomized patients in whom intubation was attempted in the analyses. We will conservatively assign all missing outcome values as the highest possible score in the control group (direct laryngoscopy) and the lowest possible score in the treatment group (McGrath videolaryngoscopy) for all primary and secondary analyses.

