## Protocol

In the preoperative period, airway details for participating patients will be recorded by a research coordinator or anesthesia provider. Patients will be positioned supine and in a standardized ramped position on the OR table. Patients will be pre-medicated with midazolam, as clinically appropriate. All patients will be pre-oxygenated until the fraction of expired oxygen exceeds 80%.

Rapid sequence induction will be induced as preferred by the attending anesthesiologist, usually with a combination of lidocaine 1 mg/kg, propofol 2-5 mg/kg, fentanyl 1-3 µg/kg, and succinylcholine 1.5 mg/kg or rocuronium 1.0 mg/kg. Complete muscle relaxation will be confirmed by absence of palpable twitches in response to supra-maximal train-of-four stimulation of the ulnar nerve at the wrist.

Patients will be randomized 1:1 before induction, stratified for primary anesthesia providers (*experienced* – specialist, attending vs. *unexperienced* – trainees) to:

- Direct laryngoscopy using an appropriately sized Macintosh blade (usually size 3 or 4);
- McGrath videolaryngoscope in an appropriate size (usually blade size 3 or 4).

Randomization will be based on computer-generated codes accessed from the Redcap system.

Intubations will be performed with a regular endotracheal tube of adequate diameter, usually 7.0 mm to 8.0 mm. Endotracheal tubes will be equipped with a hockey-stick-shaped stylette, which will be prepared by the anesthesiologist in advance. The McGrath or the Macintosh blade will be introduced into oral cavity according to manufacturer recommendations and clinical practice. Minor airway manipulation procedures including BURP or Sellick maneuvers will be allowed to improve

visualization of the vocal cords. If initial intubation attempts fail, the endotracheal tube will be removed. Minor adjustments of patient's position and/or tube stylette will be used as clinically appropriate. Up to two intubation attempts will be made as necessary. Further airway management will follow clinical assessment of the anesthesiologist. The anesthesiologist will be permitted to terminate study participation and switch to an alternative method.

Once intubation is achieved, the endotracheal tube will be connected to the anesthesia circuit, and the endotracheal cuff pressure will be measured placed between 25 and 30 cm H2O.

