#### **Primary outcome:**

Wilcoxon-Mann-Whitney test will be used to formally compare categorical outcome of glottis visualization (Cormack and Lehane classification) at the 5% significance level

between the two study groups; this test accounts for the ordinal nature of the outcome. If adjustment for imbalanced baseline covariates is required, we will attempt a proportion odds logistic regression model to compare randomized groups, reporting an odds ratio indicating the estimated odds of being better using videolaryngoscopy versus direct.

**Commented [WP1]:** See [here](#) for details on implementation and diagnostics.

If the proportional odds assumption does not hold after testing and also visualizing with further modeling, the outcome will be assessed using either an adjacent logit analysis or by combining categories and using chi-square test or binary logistic regression, as appropriate. The distribution of patients in each glottis visualization class will be reported for each randomized group.

**Commented [WP2]:** In `vgam` R package, the `acat()` function.

**Commented [WP3R2]:** Response MUST be an ordered factor. Returns an object of class vglmff to be used by vgam/vglm

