#### **Secondary outcomes:**

Randomized groups will be compared on the secondary outcome of Intubation failure (yes/no) via chi-square test and the associations reported using relative risk [97.5% confidence interval (CI)]. Randomized groups will be compared on the count of number of intubation attempts using either Wilcoxon-Mann-Whitney test or negative binomial regression, as appropriate. A Bonferroni correction will be applied and a significance criterion of  $0.05/2=0.025$  to control the overall Type I error at 5% level for two secondary hypotheses.

The exploratory and safety outcomes will be reported by study groups without formal statistical testing of the difference.

**Formatted:** Highlight

**Interim analyses** to assess efficacy and futility will be conducted at each 25% of the maximum planned enrollment. We will use a gamma spending function with gamma parameter= -4 for efficacy and -1 for futility.

**Sample size considerations.** **Sample size** is based on the primary outcome of glottis visualization (Cormack and Lehane classification) and the Wilcoxon-Mann-Whitney test. From the literature we assume a distribution of scores for the Direct Laryngoscopy group such that the proportion of patients in categories 1, 2a, 2b, 3 and 4 are 0.50, 0.30, 0.15, 0.04, 0.01, and that for the videolaryngoscopy the proportions are improved to 0.65, 0.25, 0.07, 0.02, 0.01. **We would thus need a total of 384 patients** to detect this difference or larger with 90% power at the 0.05 significance level. Incorporating a maximum of 3 interim analyses and a final analysis with the above-detailed spending functions will require a maximum **of N=438 patients**. Simulations indicate that if the specified difference is a good estimate of the true effect, the expected sample size is about 78% of the maximum sample size, or N=342. **In such a case**, the study will have a very good chance of crossing an efficacy boundary at interim looks 2 or 3.

Formatted: Font color: Red

Formatted: Font color: Red

Formatted: Font color: Light Blue

Because our estimates of laryngeal view are uncertain, **we plan to enroll a maximum of 800 patients in case the treatment effect is somewhat less than anticipated.**

Formatted: Font color: Red

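### The baseline imbalance threshold is printed upside down: at 20 to 28 pooled standard deviations it can in practice never be exceeded, so the planned covariate adjustment can never be triggered

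*Combined protocol and SAP*

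**What the plan says.** In the combined protocol and SAP, the opening paragraph of Data analysis, Statistical Analysis, measures baseline balance by the ASD, "defined as the absolute difference in means, mean ranks, or proportions divided by the pooled standard deviation". The flagging rule begins "ASD > \text{maximum of } 0.10" and its second term is "1.96 \sqrt{\frac{(n_1 n_2)}{n_1 + n_2", which reads as 1.96·√(n1n2/(n1+n2)). Characteristics over that bar "will be considered imbalanced and will be adjusted for in the primary and secondary analyses".

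The Primary outcome section makes the adjusted model depend on this rule: "If adjustment for imbalanced baseline covariates is required, we will attempt a proportion odds logistic regression model to compare randomized groups", with an odds ratio reported. Otherwise the comparison is the Wilcoxon-Mann-Whitney test. The plan gives no other trigger for covariate adjustment, no numeric value for the threshold, and no second statement of the formula that would correct it.

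**The concern.** A standardized difference has no units, and its chance variation shrinks as the arms grow. A threshold built from its standard error should shrink too. The printed term grows with the square root of the sample size, which suggests that the fraction has been inverted.

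At stake is which primary analysis is run. The rule chooses between an unadjusted rank test and an adjusted proportional odds model with an odds ratio. If the bar cannot be reached, even a gross imbalance in airway difficulty goes unadjusted, and the adjusted model described in the plan is never fitted. If an analyst silently applies the form that was probably meant, the analysis departs from the written plan at a time when baseline tables by arm are already available.

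**Working it through.** **Inputs.** Allocation is 1:1 (Protocol: "Patients will be randomized 1:1 before induction"), so n1 = n2 = N/2. The sample-size paragraph gives 384 patients for a fixed design, 438 as the group-sequential maximum, 342 expected, and 800 as maximum enrolment. The Patients section counts 25 to 50 pilot patients within the 800, and pilot patients are not analysed, which leaves 750 to 775.

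**Step 1: the plan's own figure.** The threshold has no stated value to reproduce, but the sample size that feeds it does: "We would thus need a total of 384 patients". With the two assumed category distributions, the probability that a videolaryngoscopy patient has the better view (ties counted half) is 0.5844. Noether's formula with a tie correction gives (1.960 + 1.282)² × 0.788 / (3 × 0.0844²) = 387. A Wilcoxon-Mann-Whitney odds calculation at two-sided 0.05 gives exactly 384, with power 0.9005. The sample sizes can therefore be used with confidence.

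**Step 2: the standard error.** Each arm mean, in SD units, has variance 1/n1 or 1/n2. The standard error of the difference is √(1/n1 + 1/n2) = √((n1+n2)/(n1n2)). The printed fraction is the reciprocal.

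**Step 3: both forms.**

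| Total N | Per arm | As printed: 1.96·√(n1n2/(n1+n2)) | Corrected: 1.96·√((n1+n2)/(n1n2)) |
|---|---|---|---|
| 200 | 100 | 13.9 | 0.277 |
| 342 | 171 | 18.1 | 0.212 |
| 384 | 192 | 19.2 | 0.200 |
| 438 | 219 | 20.5 | 0.187 |
| 750 | 375 | 26.8 | 0.143 |
| 800 | 400 | 27.7 | 0.139 |

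For example, at 438: 1.96 × √(219 × 219 / 438) = 1.96 × √109.5 = 20.51, and 1.96 × √(438 / 47,961) = 0.187.

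**Step 4: can the printed bar be reached?** In 10,000 simulated 1:1 randomizations of one standard normal covariate, the largest ASD was 0.40 at N = 384, 0.36 at 438 and 0.28 at 800. The printed rule flagged 0%. The corrected rule flagged 5.2%, 4.7% and 5.2%, as a 1.96 standard error criterion should. For a covariate compared on mean ranks without ties, complete separation of the arms gives a mean-rank difference of n (the number per arm) over a within-arm SD of √(n(n+1)/12). That is about √12 = 3.46, still far below the bar.

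**Step 5: the 0.10 floor.** With one patient per arm the printed term is 1.96 × √0.5 = 1.39, already above 0.10, and it only rises from there. As printed, the plan's own floor could never operate. In the corrected form with equal arms the term is 3.92/√N, which falls to 0.10 at N = 39.2² ≈ 1,537, so taking a maximum then has a purpose.

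**The case against.** The strongest reply is that this is a typographical slip that gives itself away. A floor of 0.10 makes sense only beside a term of similar size, and an analyst who computed a bar of 20 SDs would notice at once. Even on the literal reading, the result is the unadjusted Wilcoxon-Mann-Whitney test, which is the test the trial is powered on and which is valid in a randomized trial stratified by provider experience. No bias or false-positive inflation follows. Chance imbalances at these sample sizes are also modest, as the simulated maxima show. Finally, the formula was read from a PDF by a program and could have been misread.

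Much of this stands. The slip is probably typographical, Type I error is not affected, and the source PDF should be checked, although the text available shows the inverted form unambiguously. It is also true that the bar cannot be reached in practice but can be in strict mathematics. A binary covariate absent in one arm and present in all but one patient of the other would have an ASD of about 20.9 at N = 438, just above 20.5. Randomization will not produce that.

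None of this rescues the rule. Because the intended form must be guessed, two competent analysts could report different primary analyses, one following the text and one repairing it. Nor is the choice a rare one. The Measurements section lists 20 baseline items (five general and 15 airway). At about 5% each, one flag is expected by chance under the corrected rule. If the items were independent, the chance of at least one would be 1 − 0.95²⁰ = 64%; correlation among airway measures would lower that figure but not the expected count.

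**Conclusion.** The concern holds. The threshold is the reciprocal of the intended quantity. It equals 20.5 pooled SDs at 438 patients and 27.7 at 800, where 0.187 and 0.139 are meant. At smaller sizes the printed value is lower (18.1 at 342, 13.9 at 200) and the conclusion is the same. The probability that the printed rule triggers adjustment is effectively zero, so the adjusted primary and secondary analyses described in the plan would not be done.

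This rests on equal arms, on the ASD as the plan defines it, and on the extracted formula matching the source PDF. The harm is that a pre-specified analysis branch is disabled or left to the analyst's discretion. No inflation of Type I error is claimed. It must be fixed because the rule selects the primary analysis.

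**What to change.** Check the source PDF, then restate the rule as: a characteristic is imbalanced if ASD > max(0.10, 1.96·√((n1+n2)/(n1n2))). At the sample sizes in this plan the second term governs, at about 0.19 for 438 patients and 0.14 for 800.

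The cost is one corrected formula, with no change to design, sample size or data collection. The sponsor should recognise the analytic effect: with 20 baseline items the corrected rule will often flag at least one, so the primary result may often come from the adjusted proportional odds model instead of the rank test on which the sample size is based. The correction should be made and dated before outcome data are analysed by arm.

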4. BMI
5. ASA status
6. Airway examination
  - a. History of obstructive sleep apnea (yes/no)
  - b. History of snoring (yes/no)

- c. History of CPAP (yes/no)
- d. History of difficult airway (yes/no)
- e. Mobility of cervical spine (0, 15, 30, and 45 degrees)
- f. Mouth opening (cm)
- g. Inter-incisor gap (cm)
- h. Mandibular protrusion test (Class A, B, C)
- i. Thyro-mental distance (cm)
- j. Thyro-mental height (cm)
- k. Sterno-mental distance (cm)
- l. Neck circumference (cm)
- m. Upper lip bite test (Class I, II, III)
- n. Mallampati score (1/2/3/4)
- o. Teeth status (Edentulous, missing frontal teeth or full dentition)

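### Chance baseline imbalance decides both the covariates and the type of primary test; one ordinal analysis with a short, named covariate list should be fixed for all looks

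*Combined protocol and SAP*

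**What the plan says.** The Statistical Analysis section compares the arms on each baseline characteristic by absolute standardized difference (ASD). Any characteristic above the larger of 0.10 and a limit printed as 1.96·√(n1·n2/(n1+n2)) "will be considered imbalanced and will be adjusted for in the primary and secondary analyses".

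The Primary outcome section makes the Wilcoxon-Mann-Whitney test the default and then provides for a switch: "If adjustment for imbalanced baseline covariates is required, we will attempt a proportion odds logistic regression model to compare randomized groups". An odds ratio is promised for that model. On the default path only the distribution of grades per arm is promised. If proportional odds fails, the section allows an adjacent-category model or collapsed categories.

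Measurements lists 20 baseline characteristics: age, sex, race, BMI, ASA status and 15 airway items. None is named for adjustment. Randomization (Protocol section) is stratified by provider experience, which appears in no analysis.

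Interim analyses "to assess efficacy and futility will be conducted at each 25% of the maximum planned enrollment". The plan does not say whether balance is reassessed at each look, or whether the test and covariates stay fixed across looks.

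**The concern.** Covariate adjustment helps when the covariate predicts the outcome. Under randomization, the size of a baseline difference is chance and carries no information on prognostic value. The rule therefore selects on the wrong criterion: a strong predictor that happens to be balanced is ignored, and an irrelevant item that happens to differ is used.

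The same chance event also changes the kind of primary analysis. One path gives a rank test with no stated effect measure. The other gives an odds ratio conditional on whichever items were flagged. A reader cannot know in advance which result the trial will report, and the sample size was derived for only one of the two. With several looks the plan also needs to define the one statistic to which the boundaries apply, and it does not.

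**Working it through.** **1. The plan's own figures.** The inputs are in the sample size paragraph: control proportions 0.50, 0.30, 0.15, 0.04 and 0.01 for grades 1, 2a, 2b, 3 and 4, while for videolaryngoscopy "the proportions are improved to 0.65, 0.25, 0.07, 0.02, 0.01", sized "to detect this difference or larger with 90% power at the 0.05 significance level". Two-sided testing is assumed.
- P(better) = 0.65×0.50 + 0.25×0.20 + 0.07×0.05 + 0.02×0.01 = 0.3787.
- P(tie) = 0.325 + 0.075 + 0.0105 + 0.0008 + 0.0001 = 0.4114.
- Effect = 0.3787 + 0.4114/2 = 0.5844.
- The pooled proportions are 0.575, 0.275, 0.11, 0.03 and 0.01, and their cubes sum to 0.2123. The tie-corrected Noether formula gives N = (1.960 + 1.282)² × (1 − 0.2123) / (3 × 0.0844²) ≈ 387. Using the variance under the alternative as well gives 382.

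The stated 384 is reproduced. The stated maximum of 438 is also reproduced: 436 with the stated spending functions, four equal looks and non-binding futility. Both figures are for the unadjusted Wilcoxon test.

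**2. The threshold.** With equal arms:

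| N | As printed, 1.96·√(n1n2/(n1+n2)) | Inverted, 1.96·√((n1+n2)/(n1n2)) |
|---|---|---|
| 438 | 1.96×√109.5 = 20.5 | 0.187 |
| 800 | 1.96×√200 = 27.7 | 0.139 |

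No ASD will realistically reach 20. In the inverted form the 0.10 floor would matter only if 1.96×2/√N < 0.10, that is N above about 1,537. Up to 800 patients, each characteristic is therefore in effect tested at the 5% level.

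**3. Chance that the primary test is replaced (inverted form).** For 20 independent characteristics it is 1 − 0.95²⁰ = 64%. Items on the airway list overlap, so correlation was varied in simulation (20,000 runs): 54% at correlation 0.3 and 36% at 0.6. A separate check gave 55% and 35%. The range is about 35-64%.

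**4. If balance were reassessed at four equally spaced looks** (same simulation; correlation 0, 0.3, 0.6): the test type changes at least once in 65%, 67% and 58% of trials, and the covariate set in 92%, 87% and 68%. Allowing about a point for simulation error, the ranges are 58-68% and 68-93%.

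**5. Power at N=384.** The planned distributions were simulated (2,500 trials per row) with 20 independent covariates, five of them prognostic. The share of latent variance explained is an assumption, because the documents give none.

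| Variance explained | Wilcoxon | Plan's rule | Pre-specified model, five covariates |
|---|---|---|---|
| 10% | 90.3% | 90.1% | 92.6% |
| 20% | 90.2% | 90.3% | 93.9% |
| 30% | 89.8% | 89.7% | 95.9% |

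With ten covariates of no prognostic value (1,639 runs), the adjusted model had 89.0% power and Wilcoxon 89.9%, so there was no gain.

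**6. Type I error of the plan's rule.** It was 4.9-5.4% two-sided in a fixed design. Over four looks (110, 220, 330 and 438 patients), with balance reassessed each time, it was 2.1% one-sided against a 2.5% target.

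**The case against.** The strongest reply is that the rule is itself pre-specified. The trigger uses baseline data only, never outcomes, and the default test and its replacement are both written down. That stands: what is left open is which covariates enter and which test results, not the procedure.

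Three stronger readings are tempting, and the documents do not support them.
- *The error rate is inflated because the boundaries are applied to a changing statistic.* Step 6 shows no inflation.
- *The test will change from look to look.* The plan is silent on reassessment. Step 4 is conditional on that reading, and if the printed threshold is literal the test never changes.
- *The trial is underpowered.* It was sized on the unadjusted Wilcoxon test and meets its 90%. The plan forgoes a possible gain; it does not fall short of its own target.

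The objection also bears on the remedy. The planned distributions do not satisfy proportional odds exactly: the cumulative odds ratios are 1.86, 2.25, 1.70 and 1.00. If the maximum is 438, the first look has about 110 patients, with about 110×0.03 ≈ 3 at grade 3 and 110×0.01 ≈ 1 at grade 4. A null check at N=110 (4,525 runs) rejected in 5.9% for an adjusted likelihood-ratio test and 4.9% for Wilcoxon, with a simulation error of about 0.35 points. A long covariate list at that look would be unwise. This limits the size of the model but does not defend selection by imbalance.

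Finally, the printed fraction may be a fault of text extraction and should be checked in the source.

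**Conclusion.** The point holds as an analysis improvement, not as a threat to validity. On either reading of the threshold the rule does not do its job: as printed it never adjusts, and in the usual form it adjusts at random, replacing the primary test in about 35-64% of trials with 20 characteristics. Step 5 shows that it gains essentially nothing in power. A pre-specified model would gain about 2-6 points at N=384 if the chosen covariates explain 10-30% of latent variance, and nothing if they explain none.

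Apart from power, the effect measure reported for the primary outcome depends on chance imbalance. On the unadjusted path no estimate or confidence interval is promised, and the stratification factor is left out on both. The plan's silence about reassessment at interim looks should be closed in any case.

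The figures rest on treating the characteristics as continuous, on the correlations shown, and on assumed prognostic strength.

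**What to change.** Remove the imbalance trigger from both the primary and the secondary analyses, and keep the ASD table as description only, with its formula verified. Before any unblinded look, fix one ordinal primary analysis for all looks:
- a proportional odds model with treatment, the provider-experience stratum and a short list of already collected predictors, chosen on prior clinical grounds (for example Mallampati score, mouth opening, history of difficult airway);
- a list small enough for the first look (about 110 patients if the maximum is 438), with a pre-stated rule for the sparse top grades;
- the odds ratio with its confidence interval always reported;
- proportional-odds checks and the unadjusted Wilcoxon test as supporting analyses.

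State that 384 and 438 were derived for the unadjusted Wilcoxon test.

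No new data are needed. The cost is SAP text, agreement on the covariate list, and a small-sample check of the model at the first look. The odds ratio will be conditional on the chosen list.

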## Objectives and Hypothesis

Our goal is to compare conventional direct laryngoscopy using a Macintosh blade with the McGrath videolaryngoscope for rapid sequence endotracheal intubation. Specifically, we propose to test the primary hypothesis that videolaryngoscopy improves visualization of the vocal cords, defined using the modified Cormack and Lehane classification (primary outcome), versus direct laryngoscopy.

We will also test the secondary hypotheses that McGrath videolaryngoscopy decreases number of intubation attempts and the number of intubation failures. We hypothesize that the McGrath videolaryngoscopy reduces both, the number of intubation attempts and the number of intubation failures.

We will also assess the following exploratory outcomes:

1. Ease of intubation;
2. Glottis opening score (POGO) score;
3. Duration of intubation.

We will also assess the following safety outcomes:

1. Incidence of cut lips, airway injury, or dental injury;
2. Incidence of postoperative coughing;
3. Incidence or severity of postoperative sore throat;
4. Incidence or severity of postoperative hoarseness.

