## Outcomes

### Primary outcome:

Best glottis visualization, defined as visualization according to the modified Cormack and Lehane classification

Original Cormack and Lehane system	1 Full view of the glottis	2 Partial view of the glottis or arytenoids	3 Only epiglottis visible	4 Neither glottis nor epiglottis visible
View at laryngoscopy				
Modified system	1 As for original Cormack and Lehane above	2a Partial view of the glottis	2b Arytenoids or posterior part of the vocal cords only just visible	3 As for original Cormack and Lehane above

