**Secondary Outcomes:**

- Intubation attempts, defined as introducing the endotracheal tube into oral cavity to perform endotracheal intubation (1, 2, 3, etc.)
- Intubation failure, defined as
  - Failure to intubate within 3 intubation attempts
  - Need to switch intubators or intubation device
  - Need to stop study per anesthesiologist's discretion

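### The missing-outcome rule labelled conservative runs backwards: it gives missing direct-laryngoscopy patients the worst value and missing McGrath patients the best

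*Combined protocol and SAP*

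**What the plan says.** The Statistical Analysis section limits the primary and secondary analyses to randomized patients in whom intubation was attempted. It then says it will "conservatively assign all missing outcome values as the highest possible score in the control group (direct laryngoscopy) and the lowest possible score" in the other arm. The scope is explicit: "the lowest possible score in the treatment group (McGrath videolaryngoscopy) for all primary and secondary analyses".

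The direction of each scale is set elsewhere in the same document:

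- **Glottis view (primary).** The classification table runs from "1 Full view of the glottis" to "4 Neither glottis nor epiglottis visible". A higher grade is a worse view. The sample size paragraph uses the word score for these same grades: "we assume a distribution of scores for the Direct Laryngoscopy group".
- **Attempts (secondary).** "Intubation attempts, defined as introducing the endotracheal tube into oral cavity to perform endotracheal intubation (1, 2, 3, etc".). A higher count is worse, and no maximum is given.
- **Failure (secondary).** Recorded as yes or no, with no numeric coding stated.

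The primary hypothesis under Objectives and Hypothesis is that "videolaryngoscopy improves visualization of the vocal cords". The secondary hypotheses are that McGrath lowers both attempts and failures. The document does not reverse the grading, state an expected missing rate or describe any other handling of missing outcomes.

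**The concern.** A conservative rule for a superiority claim should work against the device being tested. Read with the plan's own scales, this one works for it: a missing control becomes a grade 4 and a missing McGrath patient a grade 1. Every missing value, in either arm, moves the comparison toward McGrath.

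A positive primary or secondary result could then come partly or wholly from the imputation, while the report called the handling conservative. No alternative missing-data analysis is planned that would expose this.

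**Working it through.** **Inputs from the plan.** Direct-laryngoscopy grades 1, 2a, 2b, 3, 4: 0.50, 0.30, 0.15, 0.04, 0.01. McGrath: 0.65, 0.25, 0.07, 0.02, 0.01. Wilcoxon-Mann-Whitney test at 0.05 (taken as two-sided), 1:1 allocation, 90% power; N=384 fixed, 438 with interim looks, 800 maximum. Secondary outcomes are tested at 0.025 each.

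**Step 1: reproduce the plan's sample size.** Let θ = P(control grade > McGrath grade) + ½P(tie). Summing over control grades:

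θ = 0.50×0.325 + 0.30×0.775 + 0.15×0.935 + 0.04×0.98 + 0.01×0.995 = 0.5844

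Noether's formula with tie correction, where p is the pooled grade distribution and Σp³ = 0.2123:

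N = (1.960 + 1.282)² × (1 − 0.2123) / (3 × 0.0844²) ≈ 387

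Using separate null and alternative variances gives 382. Both are close to the stated 384. Four equal looks with the stated gamma spending and non-binding futility give a maximum of 434, close to 438. The model therefore matches the plan's.

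**Step 2: apply the rule when there is no true difference.** Give both arms the direct-laryngoscopy distribution. Let a fraction m be missing in each arm, unrelated to outcome. A missing control (grade 4) against an observed patient scores 0.99 + ½×0.01 = 0.995. An observed control against a missing McGrath patient (grade 1) scores 0.50 + ½×0.50 = 0.75. Two missing patients score 1. So:

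θ = 0.5(1−m)² + m(1−m)(0.995 + 0.75) + m²

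At m = 0.02: 0.4802 + 0.0342 + 0.0004 = 0.5148. The rule alone creates a shift of 0.0148, about 18% of the design effect of 0.0844.

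**Step 3: convert to error rates.** The null standard error, with n = N/2 per arm, is √[(N+1)(1 − Σp³)/(12n²)]. At N=438 and m=0.02, Σp³ = 0.1537 and the standard error is 0.0254. The test statistic is then centred at 0.0148/0.0254 = 0.583 instead of 0. P(Z > 1.96 − 0.583) = 8.4% and P(Z < −1.96 − 0.583) = 0.5%.

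| Missing per arm | Shift in θ | N=438: false McGrath benefit | N=438: two-sided error | N=800: false McGrath benefit |
|---|---|---|---|---|
| 0% | 0 | 2.5% | 5.0% | 2.5% |
| 0.5% | 0.0037 | 3.5% | 5.2% | 3.9% |
| 1% | 0.0074 | 4.8% | 6.0% | 5.9% |
| 2% | 0.0148 | 8.4% | 9.0% | 12.1% |
| 3% | 0.0221 | 13.8% | 14.0% | 21.7% |
| 5% | 0.0366 | 30% | 30% | 49.5% |

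Simulation agrees: two-sided error at N=438 of about 6%, 9%, 14% and 30% at 1%, 2%, 3% and 5% missing. At 1% missing about 80% of the error (4.8 of 6.0 points) favours McGrath; from 2% upward nearly all of it does.

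**Step 4: with the planned interim looks** (non-binding bounds, trial stops at futility), simulated false McGrath benefit is:

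| Missing per arm | N=438 | N=800 |
|---|---|---|
| 0% | 2.2% | 2.1% |
| 1% | 4.2% | 5.1% |
| 2% | 7.3% | 10.4% |
| 5% | 26.5% | 44.5% |

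**Step 5: intubation failure** (219 per arm, nominal 1.25% per side, yes coded above no). The plan gives no failure rate, so 2% and 5% are assumed. With random missingness and an uncorrected chi-square test, false McGrath benefit is 3.6% to 5.0% at 1% missing and 8.6% to 14.2% at 2%. With a continuity correction it is 2.0% to 2.4% and 5.3% to 8.8%. With a fixed number missing per arm (2 or 4 of 219), uncorrected, it is 2.9% to 3.7% and 6.3% to 9.7%.

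**Step 6: reverse the rule** (control grade 1, McGrath grade 4), N=438, single look. False McGrath benefit falls to 1.2% at 1% missing and 0.5% at 2%, below the nominal 2.5%. Power at the design effect falls from 93.5% to 88% and 79%. At N=800 with 2% missing it falls from 99.7% to 96%.

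**The case against.** The strongest reply is that this is a slip of wording. The section says the rule is conservative, so the authors may have meant highest as best view, and an analyst might apply it that way. That may well be the intent. But the plan uses score for grades 1 to 4, and a programmer following the text would code grade 4 for missing controls. The sentence needs correcting either way.

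Second, missingness may be very low. The analysis set requires an attempted intubation, and view, attempts and failure are all recorded during the procedure, with no follow-up visit. This stands as a limit on size: at 0.5% missing, two-sided error at N=438 is only 5.2%, and nothing in the documents supports 5% missing. It does not change the direction. The protocol also lets the anesthesiologist end study participation and switch method, so gaps could fall in difficult cases.

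Third, for failure the direction depends on coding yes above no, and for attempts the highest possible value is undefined. Both are true. They are further reasons to rewrite the sentence.

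Fourth, single-look figures are not for the planned design. With the looks the inflation is slightly smaller, as Step 4 shows, but it remains.

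**Conclusion.** The concern holds. As written, the rule favours McGrath in the primary analysis and in attempts, and in failure under the usual coding, which contradicts its label. Any missing outcome biases the comparison in that direction. More patients make the false-positive rate worse, because the shift is fixed by the missing rate while the standard error shrinks.

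The size depends on a missing rate the plan does not give. It is nil at 0%, small at 0.5%, and at 2% missing per arm the false-benefit rate is about three to five times its nominal 2.5% (7.3% to 12.1%, across N=438 and N=800, with and without interim looks). These figures assume equal missingness in both arms, unrelated to outcome. The sample sizes of 384 and 438 do not depend on the rule and are unaffected. This must be corrected before analysis.

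**What to change.** Rewrite the sentence and name the values instead of using highest and lowest. At minimum, swap the arms: missing direct-laryngoscopy outcomes get grade 1, one attempt and no failure; missing McGrath outcomes get grade 4, a stated maximum number of attempts, and failure.

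That maximum has to be defined. The Protocol section allows up to two attempts, while the failure definition refers to three; these passages must be reconciled first.

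The better choice is to make observed data or multiple imputation the primary analysis and keep the swapped rule as a prespecified sensitivity analysis. The swapped rule is itself biased, against McGrath: by symmetry, at N=438 with 2% missing and no true difference, it gives an 8.4% chance of a false finding for direct laryngoscopy. It also costs the power shown in Step 6. Complete-case analysis at the same 2% keeps power at about 93%.

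The number missing per arm and the reasons should be reported. The cost is a short SAP edit, made before unblinded data are seen, with no change to sample size or data collection.
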